6.5.4.4 Urinary albumin creatinine ratio (UACR)

For CKD patients, UACR will be measured from 3 consecutive early morning urine collections, beginning 3 days prior to the scheduled visit (see [Table 6-1](#)). UACR will be measured at Visits 2, 5, 10, and 11.

Urine collection materials and instructions will be provided to the patients prior to their visit. The patients will collect these three samples on the three days prior to their study visit and they will bring them when they return to the site. A central laboratory will be used for analysis of UACR samples. Details on the collections, shipment of samples and reporting of results by the central laboratory are provided to investigators in the laboratory manual. UACR will be calculated as follows:

$$\text{UACR [mg/mmol]} = \text{urine albumin [mg/L]} / \text{urine creatinine [mmol/L]}$$

6.5.4.5 Estimated Glomerular filtration rate (eGFR)

Schwartz GFR

For all patients, eGFR will be calculated using the Modified Schwartz Formula (Schwartz et. al 1976). This formula to estimate eGFR uses serum creatinine, height and a constant depending on age and gender:

$$\text{eGFR [ml/min/1.73m}^2\text{]} = \text{k} * \text{Height [cm]} / \text{Serum Creatinine [mg/dL]}$$

Age	K
< 1 year	0.45
1 to 12 years	0.55
13 to 20 years (adolescent females)	0.55
13 to 20 years (adolescent males)	0.70

[\(Schwartz et al 1976\)](#)

Cystatin C eGFR

For CKD patients, the eGFR will also be calculated using the cystatin C value.

A serum cystatin C sample will be collected and the GFR will be estimated with the following formula [\(Filler et al 2003\)](#):

$$\text{Log GFR [ml/min/1.73m}^2\text{]} = 1.962 + [1.123 * \log (1 / \text{serum cystatin C})]$$

6.5.5 Electrocardiogram (ECG)

A standard 12-lead ECG will be performed at Visits 1, 5, and 11. The tracings will be dated and signed by the physician who provides the clinical interpretation of the ECG. The patient's identification number, the date and actual time of the tracing, and the study code "Study CVAL489K2306" must appear on each ECG tracing. In the CRF any ECG abnormalities will be recorded.

6.5.6 Pregnancy and assessments of fertility

Not applicable

6.5.7 Appropriateness of safety measurements

The safety assessments selected are standard for this indication/patient population.

6.6 Other assessments

Parents of the patients will be given a taste assessment at the final study visit. Investigator staff will ask the parent to evaluate how their child interpreted the taste of the study medication throughout the trial. The study staff will document this information in the patient's source document and complete this on the End of Study Case Report Form.

6.6.1 Resource utilization

Not applicable

6.6.2 Health-related Quality of Life

Not applicable

6.6.3 Pharmacokinetics

Not applicable

6.6.4 Pharmacogenetics/pharmacogenomics

Not applicable.

6.6.5 Other biomarkers

Not applicable

7 Safety monitoring

7.1 Adverse events

An adverse event (AE) is any untoward medical occurrence (i.e., any unfavorable and unintended sign [including abnormal laboratory findings], symptom or disease) in a subject or clinical investigation subject *after providing written informed consent* for participation in the study. Therefore, an AE may or may not be temporally or causally associated with the use of a medicinal (investigational) product. Medical conditions/diseases present before starting study drug are only considered adverse events if they worsen after starting study drug.

The occurrence of adverse events should be sought by non-directive questioning of the patient at each visit during the study. Adverse events also may be detected when they are volunteered by the patient during or between visits or through physical examination, laboratory test, or other assessments.

Abnormal laboratory values or test results constitute adverse events only if they fulfill at least one of the following criteria:

- they induce clinical signs or symptoms,
- they are considered clinically significant,
- they require therapy.

Clinically significant abnormal laboratory values or test results should be identified through a review of values outside of normal ranges/clinically notable ranges, significant changes from baseline or the previous visit, or values which are considered to be non-typical in patient with underlying disease. Investigators have the responsibility for managing the safety of individual patient and identifying adverse events. Alert ranges for labs and other test abnormalities are included in [Appendix 1](#)

Adverse events should be recorded in the Adverse Events CRF under the signs, symptoms or diagnosis associated with them accompanied by the following information.

- the severity grade
 - mild: usually transient in nature and generally not interfering with normal activities
 - moderate: sufficiently discomforting to interfere with normal activities
 - severe: prevents normal activities

All adverse events must be recorded on the Adverse Events CRF with the following information:

1. the severity grade (mild, moderate, severe)
2. its relationship to the study drug (suspected/not suspected)
3. its duration (start and end dates or if continuing at final exam)
4. to action taken regarding study treatment
5. whether it constitutes a serious adverse event (SAE)
6. whether other medication or therapies have been taken (concomitant medication/non-drug therapy)
7. its outcome (continuing/not continuing)

An SAE is defined as an event which:

- is fatal or life-threatening
- results in persistent or significant disability/incapacity
- constitutes a congenital anomaly/birth defect
- requires inpatient hospitalization or prolongation of existing hospitalization, unless hospitalization is for:
 - routine treatment or monitoring of the studied indication, not associated with any deterioration in condition
 - elective or pre-planned treatment for a pre-existing condition that is unrelated to the indication under study and has not worsened since the start of study drug
 - treatment on an emergency outpatient basis for an event not fulfilling any of the definitions of a SAE given above and not resulting in hospital admission

- social reasons and respite care in the absence of any deterioration in the patient's general condition
- is medically significant, i.e. defined as an event that jeopardizes the patient or may require medical or surgical intervention to prevent one of the outcomes listed above

All malignant neoplasms will be assessed as serious under "medically significant" if other seriousness criteria are not met.

Unlike routine safety assessments, SAEs are monitored continuously and have special reporting requirements; see [Section 7.2](#).

All adverse events should be treated appropriately. Treatment may include one or more of the following: no action taken (i.e. further observation only); study drug dosage adjusted/temporarily interrupted; study drug permanently discontinued due to this adverse event; concomitant medication given; non-drug therapy given; patient hospitalized/patient's hospitalization prolonged. The action taken to treat the adverse event should be recorded on the Adverse Event CRF.

Once an adverse event is detected, it should be followed until its resolution or until it is judged to be permanent, and assessment should be made at each visit (or more frequently, if necessary) of any changes in severity, the suspected relationship to the study treatment, the interventions required to treat it, and the outcome.

Information about common side effects already known about the investigational drug can be found in the Investigator Brochure (IB) or will be communicated between IB updates in the form of Investigator Notifications. This information will be included in the patient informed consent and should be discussed with the patient during the study as needed.

The investigator should also instruct each patient to report any new adverse event (beyond the protocol observation period) that the patient, or the patient's personal physician, believes might reasonably be related to study treatment. This information should be recorded in the investigator's source documents, however, if the AE meets the criteria of an SAE, it must be reported to Novartis.

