5.5.9 Discontinuation of study treatment and premature patient withdrawal

Patients may voluntarily withdraw from the study for any reason at any time. They may be considered withdrawn if they state an intention to withdraw, fail to return for a visit or become lost to follow up for any other reason.

If premature withdrawal occurs for any reason, the investigator must make every effort to determine the primary reason for a patient's premature withdrawal from the study and record this information on the Study Completion CRF.

The investigator should discontinue study treatment for a given patient or withdraw the patient from the study if, on balance, he/she believes that continuation would be detrimental to the patient's well-being.

Study drug must be discontinued for a given patient if the investigator determines that continuing it would result in a significant safety risk for that patient. If one of the following applies, the patient should be thoroughly evaluated by the Investigator within 48 hours, and should be discontinued from study drug.

- Withdrawal of informed consent
- MSBP is $>25\%$ above the 95th percentile for age, gender and height at any time during the study after baseline
- Symptomatic hypotension and MSBP $\leq 50^{\text{th}}$ percentile for gender, age and height at any time during the study
- Any of the following laboratory abnormalities:
 - If patient has an eGFR $<30 \text{ mL/min}/1.73\text{m}^2$, the patient will need a repeat lab test, advisable within one week after results were sent. If the repeat value confirms eGFR $<30 \text{ mL/min}/1.73\text{m}^2$, the patient must be discontinued per valsartan label
 - $>50\%$ decrease in eGFR from baseline
 - Severe anemia: defined as hemoglobin $<9 \text{ g/dL}$
 - WBC $<3000/\text{mm}^3$
- Hyperkalemia: If a serum potassium level is $>5.3 \text{ mmol/L}$ (as per central lab), the patient will need a repeat lab test, advisable within one week after results were sent. All patients with serum potassium of 5.3 mmol/L or higher should be followed and appropriate medical care given.
If the repeat value confirms serum potassium $> 5.5 \text{ mmol/L}$ (as per central lab), the patient must be immediately discontinued from the study and the appropriate medical care given.
- Liver function monitoring:

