9.5.3 Safety variables

The assessment of safety will be based mainly on the frequency of adverse events and on the summary of laboratory values for the safety populations. Other safety data (e.g. weight, height, resting pulse and head circumference) will be summarized as appropriate. The safety (SAF) and open-label safety (OSAF) populations will be used as appropriate for summaries of the double-blind and open-label periods.

Adverse events newly occurring or worsening during the double-blind treatment period and open-label period will be summarized by primary system organ class, preferred term, and treatment (only for double-blind period). Suspected study-drug related adverse events will be summarized similarly.

Serious adverse events and adverse events leading to study drug discontinuation (based on CRF AE data) will be summarized by primary system organ class, preferred term, and treatment, and will be listed by patient.

Laboratory data will be summarized by treatment for change from baseline and for occurrence of abnormality as appropriate.

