9.7.1.3.1 Adverse Events

The number and percentage of patients reporting any adverse event during the double-blind treatment period and open-label phase will be summarized by primary system organ class, preferred term, and treatment (only for double-blind phase). Adverse events that are suspected to be related to study drug will be summarized. The maximum severity of all adverse events will be summarized. Serious adverse events and adverse events leading to study drug discontinuation (based on CRF AE data) will be summarized by primary system organ class, preferred term, and treatment (only for double-blind phase), and will be listed by patient.

In addition, all summaries will also be performed for the subgroups of CKD and non-CKD patients for double-blind phase and open-label phase, respectively.

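### A laboratory value that stops study drug under Protocol 5.5.9 is not automatically an adverse event, so the table of AEs leading to discontinuation can miss some laboratory-mandated stops, chiefly in the open-label period

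*Protocol*

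**What the plan says.** Protocol 7.1 limits when a laboratory finding is an adverse event: "Abnormal laboratory values or test results constitute adverse events only if they fulfill at least one of the following criteria". The three criteria are that it produces clinical signs or symptoms, that "they are considered clinically significant", or that it needs therapy. Clinical significance is to be found by reviewing values outside normal or notable ranges, significant changes from baseline or the previous visit, or "values which are considered to be non-typical in patient with underlying disease". The decision rests with the site: "Investigators have the responsibility for managing the safety of individual patient and identifying adverse events".

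Protocol 5.5.9 lists events after which the child is to be evaluated within 48 hours "and should be discontinued from study drug". The laboratory entries are eGFR <30 confirmed on repeat, a >50% fall in eGFR from baseline, hemoglobin <9 g/dL ("Severe anemia: defined as hemoglobin" below that value), WBC <3000/mm3, potassium >5.5 mmol/L confirmed on repeat, and liver tests >3 x ULN on retest. The section also requires a Study Drug Discontinuation form giving the date and primary reason.

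For reporting, SAP 9.7.1.3.1 states that "adverse events leading to study drug discontinuation (based on CRF AE data) will be summarized by primary system organ class", and Protocol 9.5.3 has the same restriction to AE form data. SAP 9.7.1.1 summarises disposition by period.

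**The concern.** Neither 5.5.9 nor 7.1 says that a value crossing a stop limit is by that fact an AE or must be entered on the AE form. A site can stop drug as 5.5.9 requires, complete the discontinuation form, and record no AE, all within the protocol. The stop then drops out of the one safety table that names discontinuation, and whether it does so depends on the investigator's opinion.

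Hyperkalemia is an identified risk in Protocol 3.6, at least half the children are to have CKD, and safety with and without CKD is a secondary objective (Protocol 2.2). A display of safety stops that may be incomplete for laboratory causes weakens the evidence on that objective.

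**Working it through.** The plan gives no figure to reproduce. The check sets the stop limits against the two SAP laboratory displays that might catch what the AE table misses, and then places the stops in time.

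**Step 1. Coverage.** Stop limits are from Protocol 5.5.9; displays are from SAP 9.7.1.3.2.

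| Stop limit | Absolute count in SAP Table 3 | Notable percentage change |
|---|---|---|
| Hemoglobin <9 g/dL | none | >30% decrease |
| WBC <3000/mm3 | none | >50% decrease |
| eGFR <30, confirmed | none | >25% decrease |
| eGFR fall >50% | none | always within >25% decrease |
| Potassium >5.5 mmol/L, confirmed | yes, >5.5 | >20% increase |
| Liver tests >3 x ULN on retest | yes, SGOT/SGPT >3 x and bilirubin >2 x | >150% (SGOT, SGPT), >100% (bilirubin) increase |

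The last three rows are counted somewhere. The first three depend on the percentage-change column.

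**Step 2. When does a stop value also reach the notable change?** A value just below limit L, from baseline B, is a fall of about (B - L)/B. It exceeds fraction p only if B > L/(1 - p).

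- Hemoglobin: 9/(1 - 0.30) = 12.86 g/dL, about 12.9
- WBC: 3000/(1 - 0.50) = 6000/mm3
- eGFR: 30/(1 - 0.25) = 40 mL/min/1.73m2

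Protocol 4.2 admits screening values down to the stop limits themselves, so the baselines at which a just-below-limit stop goes unflagged are roughly 9 to 12.9 g/dL, 3000 to 6000/mm3 and 30 to 40 mL/min/1.73m2. Illustrative values (assumed, not from the documents) that meet a stop limit but appear in neither count:

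- Hemoglobin 10.5 to 8.9: 1.6/10.5 = 15.2% fall
- WBC 5000 to 2900: 2100/5000 = 42.0% fall
- eGFR 38 to 29: 9/38 = 23.7% fall

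None of the counts in either display is tied to discontinuation.

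**Step 3. Which period?** Protocol 6.5.4.1 and 6.5.4.2 schedule hematology and chemistry at Visits 1, 2, 5, 8, 9, 10 and 11 (abbreviated chemistry at 9 and 10). The first dose is at Visit 2. Visit 5 (Week 6) is therefore the only scheduled post-dose draw in Period 1, and it falls at its end, when every child moves to open-label drug (Protocol 3.1). Samples go to a central laboratory (Protocol 6.5.4), so action on a Visit 5 result would normally follow in Period 2. In Period 1 only an unscheduled sample, or a Visit 2 result that arrived after dosing, could lead to such a stop. SAP 9.7.1.3.1 splits its discontinuation table by treatment for the double-blind phase only.

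**The case against.** The strongest reply is that the gap is narrow in practice. 7.1 offers three routes to clinical significance joined by "or" in sense, so a CKD child's value need not be atypical for the disease if it is out of range or has changed significantly. Because Protocol 4.2 excludes values beyond most of these limits at screening, a later crossing is a worsening. 5.5.9 requires an evaluation by the investigator and names anemia and hyperkalemia as conditions. Confirmed potassium >5.5 calls for medical care, which may meet the therapy criterion. Stopping a child for a value judged not clinically significant is possible but strained. Disposition summaries, shift tables, listings and the discontinuation form also mean that no data are lost. All of this stands and limits the weight of the point. It does not close the gap: no text links a stop limit to the AE form, and no table of stops by laboratory criterion, or reconciliation of the two forms, is planned.

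The reply also notes that a table of AEs by system organ class should use AE data, and that Protocol 8.3 provides MedDRA coding for AEs and medical history only. That is right, and the remedy should be a separate table.

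A reader might infer that the randomised-dose comparison of safety stops is materially distorted. The laboratory schedule does not support that, as Step 3 shows. A reader might also try to estimate missed stops per arm from an assumed within-child hemoglobin variability, since the entry and stop limits coincide. The documents give neither that variability nor the spread of baselines, and the chance of a value below 9 is not the chance of a stop with no AE recorded.

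**Conclusion.** The point holds as a reporting gap of modest size. The table of AEs leading to discontinuation can omit laboratory-mandated stops, mainly those for hemoglobin <9, WBC <3000 and eGFR <30. For these the other laboratory displays are also incomplete when baseline lies below about 12.9 g/dL, 6000/mm3 or 40 mL/min/1.73m2. Potassium and liver stops, and eGFR falls >50%, are counted in the laboratory tables, though not as discontinuations.

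The consequence is chiefly for the single-arm open-label summaries. How many stops would be missed cannot be computed from the documents. The conclusion rests on the wording of 7.1, 5.5.9, 9.5.3 and the SAP, and on the Step 2 arithmetic for values just below a limit; a larger fall from the same baseline could be flagged.

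**What to change.** In Protocol 7.1, state that a laboratory value leading to interruption or discontinuation of study drug is recorded on the AE form.

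In the SAP:

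- Keep the table of AEs leading to discontinuation as it is.
- Add a separate table of discontinuations by 5.5.9 laboratory criterion, taken from the Study Drug Discontinuation form and reconciled with the AE form, by treatment in Period 1 and by current dose in Period 2.
- Add counts of eGFR <30, hemoglobin <9 and WBC <3000 to Table 3, and widen its lead-in, which now refers to biochemistry only.

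The cost is slightly more AE entries, one more table and three more rows. The discontinuation form is already collected. No stopping rule or threshold changes.

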7.2 Serious adverse event reporting

To ensure patient safety, every SAE, regardless of suspected causality, occurring after the patient has provided informed consent and until 30 days after the patient has stopped study participation (defined as time of last dose of study drug taken or last visit whichever is later).must be reported to Novartis within 24 hours of learning of its occurrence. Any SAEs experienced after the 30 days period should only be reported to Novartis if the investigator suspects a causal relationship to study treatment.

Recurrent episodes, complications, or progression of the initial SAE must be reported as follow-up to the original episode, regardless of when the event occurs. This report must be submitted within 24 hours of the investigator receiving the follow-up information. An SAE that is considered completely unrelated to a previously reported one should be reported separately as a new event.

Information about all SAEs is collected and recorded on the Serious Adverse Event Report Form. The investigator must assess the relationship of any SAE to study treatment, complete the SAE Report Form in English, and send the completed, signed form by fax within 24 hours to the local Novartis Drug Safety and Epidemiology Department. The telephone and fax number of the contact persons in the local department of Drug Safety and Epidemiology, specific to the site, are listed in the investigator folder provided to each site. The original copy of the SAE Report Form and the fax confirmation sheet must be kept with the case report form documentation at the study site. Follow-up information should be provided using a new paper SAE Report Form stating that this is a follow-up to a previously reported SAE.

Follow-up information provided should describe whether the event has resolved or continues, if and how it was treated, whether the treatment code was broken or not and whether the patient continued or withdrew from study participation. Each re-occurrence, complication, or progression of the original event should be reported as a follow-up to that event regardless of when it occurs.

If the SAE is not previously documented in the Investigator's Brochure or Package Insert (new occurrence) and is thought to be related to the investigational treatment a Drug Safety and Epidemiology Department associate may urgently require further information from the investigator for Health Authority reporting. Novartis may need to issue an Investigator Notification (IN) to inform all investigators involved in any study with the same investigational treatment that this SAE has been reported. Suspected Unexpected Serious Adverse Reactions (SUSARs) will be collected and reported to the competent authorities and relevant ethics committees in accordance with Directive 2001/20/EC or as per national regulatory requirements in participating countries.

7.3 Liver safety monitoring

To ensure patient safety and enhance reliability in determining the hepatotoxic potential of an investigational drug, a standardized process for identification, monitoring and evaluation of liver events has to be followed.

- Repeating the LFT to confirm elevation as appropriate
- Discontinuation of the investigational drug if appropriate; see to [section 5.5.9](#)
- Hospitalization of the patient if appropriate
- A causality assessment of the liver event via exclusion of alternative causes (e.g., disease, co-medications)
- An investigation of the liver event which needs to be followed until resolution.

These investigations can include serology tests, imaging and pathology assessments, hepatologist's consultancy, based on investigator's discretion. All follow-up information, and the procedures performed should be recorded on appropriate CRF pages.

